15.2 Sample Size Calculations

The rate of grade 3 or higher neutropenia in PALOMA -1 and PALOMA – 3 was 54% and 62% respectively. We anticipate the new schedule to have less toxicity leading to around 40%-50% AE rate. The sample size was calculated to test the one-sided null hypothesis that 1-AE (adverse event) rate ≤ 0.38 (i.e., AE rate >0.62) versus the alternative that 1-AE rate ≥ 0.6 (i.e., AE rate <0.4). Enrollment of 47 patients will be required to achieve 90% power (actual power=91.8%) based on one-sample binomial exact test at a 5% level (actual alpha=4.7%). If no grade 3 or higher adverse events were observed on 24 or more patients on the alternative dosing schedule, the alternative dosing will be deemed to show better toxicity profile than standard schedule.

The CBR was estimated as 84.3% (80%~88%) in 1st line and 67% from PALOMA-3 in 2nd line patients. With an estimation that 70% of the enrolled patients are 2nd line, we expect approximately 33 2nd line patients and 14 1st line patients and thus ~22 2nd line patients with ~11 1st line patients with clinical benefit. With 33 2nd line patients, the CBR can be estimated with a 95% two-sided Clopper-Pearson exact CI of 48.5~82.3% given the true CBR is 67% as in PALOMA-3 while the CBR in the 14 1st line patients can be estimated with a 95% CI of 55.5%~97.7% given the true CBR is 84.3%.

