A randomized phase 3 study to confirm the efficacy of palbociclib in combination with letrozole in this setting (PALOMA2) was recently reported at ASCO 2016 annual meeting and again demonstrated a significant improvement in progression free survival (PFS): 24.8 (22.1-NR) months in the palbociclib/letrozole arm vs 14.5 (12.9-17.1) months in the placebo/letrozole arm, HR 0.58; $p < 0.000001$ (12). Among the 444 patients treated with palbociclib and letrozole, neutropenia (any grade) occurred in 80% of patients vs. 6% in the placebo/letrozole arm. The incidence of grade 3 and 4 neutropenia in the palbociclib/letrozole arm was 56% and 10%, respectively. Grade 3 or 4 non-hematological AEs were uncommon. 9.7% of patients in the palbociclib/letrozole arm vs 5.9% in the placebo/letrozole arm discontinued treatment due to AEs (12).

Most recently, a randomized phase 3 study (PALOMA3) assessed the safety and efficacy of the combination of palbociclib and fulvestrant vs placebo and fulvestrant after disease progression after prior endocrine therapy in premenopausal and postmenopausal women with hormone receptor positive and Her-2/neu negative advanced breast cancer. In this study, premenopausal females also received goserelin for ovarian suppression. A significantly prolonged PFS was noted with the combination of palbociclib and fulvestrant compared with fulvestrant and placebo. The dosing schedule of palbociclib was 125 mg po daily for 3 weeks followed by one week off drug (13).

Similar to PALOMA2, most common hematologic adverse events reported for the palbociclib–fulvestrant group in PALOMA3 were neutropenia and leukopenia. Neutropenia (any grade) occurred in 78.8% of the patients receiving palbociclib–fulvestrant versus 3.5% in the placebo–fulvestrant group, leukopenia in 45.5% versus 4.1%, anemia in 26.1% versus 9.9%, and thrombocytopenia in 19.4% versus 0%. Grade 3 or 4 neutropenia occurred in 62.0% of the patients receiving palbociclib–fulvestrant versus 0.6% of the patients receiving placebo–fulvestrant, leukopenia in 25.2% versus 0.6%, anemia in 2.6% versus 1.7%, and thrombocytopenia in 2.3% versus 0%. The most common nonhematologic adverse events were fatigue, nausea (29.0% vs. 26.2%), and headache, all of which were more common in the palbociclib-fulvestrant group. A higher incidence of infections was also reported in the palbociclib–fulvestrant group (13).

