2.0 OBJECTIVES

2.1 Primary Objective

To determine the rate of grade 3 or higher neutropenia in patients with hormone receptor positive breast cancer treated with palbociclib on a 5 days on/2 days off schedule within the first 29 days of treatment.

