2.2 Secondary Objectives

1. To determine the rate of grade 3 or higher neutropenia in patients with hormone receptor positive breast cancer treated with palbociclib on a 5 days on/2 days off schedule during all cycles.
2. To determine the rate of palbociclib dose reduction, interruption, or discontinuation.
3. To determine the adverse events profile of palbociclib given on a 5 days on/2 days off schedule.
4. To determine the progression free survival in patients with hormone receptor positive breast cancer treated with palbociclib on a 5 days on/2 days off schedule.
5. To determine the overall response rate (CR+PR) in patients with hormone receptor positive breast cancer treated with palbociclib on a 5 days on/2 days off schedule.
6. To determine the clinical benefit rate (CR+PR+SD for at least 6 months) in patients with hormone receptor positive breast cancer treated with palbociclib on a 5 days on/2 days off schedule.

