15.0 STATISTICAL CONSIDERATIONS

15.1 Study Description

This is a single arm phase II clinical trial with metastatic HR+ HER2- breast cancer patients treated by palbociclib on a 5 days on/2 days off schedule.

The primary endpoint of the trial is the rate of grade 3 or higher adverse events (AE rate) within the first 29 days (equivalently, 1-AE rate, i.e., the proportion of patients not suffering grade 3 or 4 AEs) The secondary endpoints include AE rate in all cycles, rate of palbociclib dose reduction or interruption or discontinuation, AE profiles, PFS, ORR, and clinical benefit rate.

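### The 24-of-47 rule is correct against a 62% null, but its event and its unwindowed benchmark do not support a claim of better toxicity than the standard schedule

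*Combined protocol and SAP*

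**What the plan says.** The primary objective (section 2.1) is the rate of grade 3 or higher neutropenia "on a 5 days on/2 days off schedule within the first 29 days of treatment". Section 15.1 gives the primary endpoint as "the rate of grade 3 or higher adverse events (AE rate) within the first 29 days". The rate "on a 5 days on/2 days off schedule during all cycles" is a separate, secondary objective (section 2.2).

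Section 15.2 takes its benchmark from earlier trials of the standard schedule: "The rate of grade 3 or higher neutropenia in PALOMA -1 and PALOMA – 3 was 54% and 62% respectively". The test is set up to "test the one-sided null hypothesis that 1-AE (adverse event) rate ≤ 0.38 (i.e., AE rate >0.62"), against an alternative event rate of 40%, with 47 patients. If 24 or more patients have no grade 3 or higher adverse event, "the alternative dosing will be deemed to show better toxicity profile than standard schedule".

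Section 1.2 repeats the PALOMA-3 figure ("Grade 3 or 4 neutropenia occurred in 62.0% of the patients receiving" the combination) and adds PALOMA-2: "The incidence of grade 3 and 4 neutropenia in the palbociclib/letrozole arm was 56% and 10%, respectively". None of these rates is given with a time window. The trial has one arm, so the 62% constant is the only comparator.

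**The concern.** The calculation in section 15.2 controls the error of one statement: that the event rate is below 62%. The conclusion attached to it is a different statement, that the new schedule is less toxic than the standard one. To get from one to the other, two things must match.

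- **The event.** The benchmark is a neutropenia rate. The rule, read literally, counts patients free of any grade 3 or higher adverse event. Other grade 3 events would then count against the new schedule when none are counted in the benchmark.
- **The window.** The endpoint stops at 29 days. The protocol itself treats the 29-day rate and the all-cycle rate as different quantities, yet it does not say which of the two the 62% is.

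At stake is the trial's main conclusion. The first mismatch could make a useful schedule fail. The second could let a schedule that is no better pass.

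**Working it through.** **Inputs.** From section 15.2: 47 patients, pass at 24 or more event-free, null event rate 62%, alternative 40%, PALOMA-1 rate 54%, PALOMA-3 rate 62%. From section 1.2: PALOMA-2 grade 3 and grade 4 rates of 56% and 10%, which sum to 66% if they are exclusive worst grades (assumed). Also assumed, because the documents give no figure: other grade 3 or higher events add 5 or 10 percentage points to the neutropenia rate.

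**Formula.** For a true event rate r,

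P(pass | r) = Σ over x = 24 to 47 of C(47, x) (1 − r)^x r^(47 − x).

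**Step 1: the plan's own figures.** P(pass | 0.62) = 0.0466 and P(pass | 0.40) = 0.9181. Both stated values, 4.7% and 91.8%, reproduce. Neighbouring cut-offs do not match: 23 gives alpha 8.3%, and 25 gives alpha 2.4% with power 86.4%.

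**Step 2: the event.** Suppose the new schedule reaches a 40% neutropenia rate and the rule is applied literally.

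| Assumed addition from other events | r | P(pass) |
|---|---|---|
| none | 0.40 | 91.8% |
| 5 points | 0.45 | 75.5% |
| 10 points | 0.50 | 50.0% |

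Error moves the safe way on this reading. If the neutropenia rate is 62%, the any-event rate is at least 62%, so P(pass) is at most 4.7%.

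**Step 3: the benchmark.** Take the event as neutropenia, and let the new schedule's 29-day rate equal the standard schedule's. Passing is then a false claim of superiority.

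| Standard 29-day rate | Where the figure comes from | P(pass) |
|---|---|---|
| 54% | PALOMA-1, section 15.2 | 29.0% |
| 60% | illustration | 8.2% |
| 62% | PALOMA-3, sections 1.2 and 15.2 | 4.7% |
| 66% | PALOMA-2, section 1.2 (56% + 10%) | 1.2% |

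Setting P(pass | r) = 0.05 gives r = 0.6176, so the error exceeds 5% for any standard 29-day rate below about 61.8%. The rule has almost no slack around 62%.

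**Step 4: direction of the window mismatch.** In the same patients, a 29-day rate cannot exceed a whole-treatment rate. If 62% is a whole-treatment rate, the mismatch can therefore only help the new schedule. The documents give neither the window nor onset times, so the size cannot be computed and may be near zero.

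**Step 5: what the data can say at the cut-off.** With 24 event-free there are 23 events, and 23/47 = 48.9%. The one-sided exact 95% upper limit is the 0.95 quantile of Beta(24, 24), which is 61.8%. The two-sided exact 95% interval is 34.1% to 63.9%. It still contains 62% although the test has passed, so the one-sided limit is the one that agrees with the rule.

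**The case against.** The strongest reply is that nothing here is shown to be wrong, only left unstated. The 62% is sourced to a cited trial, whose window the sponsor can look up. If most events occur early, the 29-day and whole-treatment rates nearly coincide. Against PALOMA-2's 66% the rule is conservative. Every single-arm phase II trial leans on a historical constant, and the conclusion can be read as a go/no-go label. The all-cycle rate will be reported with a 95% interval in any case (section 15.3).

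Much of this stands. The arithmetic is sound, the window effect may be negligible, and dependence on a fixed null comes with the design. A reader might infer that the true type I error is inflated because 62% is a whole-treatment rate. The documents do not support that: they never state the window, and their own rates give errors from 1.2% to 29.0%.

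Two things remain. The difference between neutropenia and any adverse event is on the page and needs no outside source. And section 15.2 itself cites 54% beside 62%, tests only against the higher value, and then concludes about the standard schedule in general. The all-cycle rate gives context but has no part in the decision rule.

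**Conclusion.** The stated alpha and power are correct for a 62% null. The rule as written does not support a conclusion about the standard schedule.

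- Read literally, it tests a broader event than the objective and the benchmark. Under the assumed additions of 5 and 10 points, power at a 40% neutropenia rate drops from 91.8% to 75.5% and 50.0%.
- Read as neutropenia, its error against the standard schedule is at most 5% only if that schedule's 29-day rate is at least about 61.8%. No visible passage states or justifies this. Across the rates that the documents cite, the error is 1.2%, 4.7% or 29.0%, each taken as a 29-day rate and as a known constant.

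It would be tempting to say that the two mismatches cancel, since they push in opposite directions. Neither has a size in the documents, so cancellation cannot be claimed. This should be fixed; confidence is medium, because the effect of the window may be near zero.

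**What to change.** 1. In sections 15.1 and 15.2, define the primary endpoint and the 24-of-47 rule by grade 3 or higher neutropenia within the first 29 days, to match section 2.1 and the benchmark.
2. Keep 47 patients and the cut-off of 24. Word the conclusion as: the 29-day grade 3 or higher neutropenia rate is below 62%.
3. Report beside it the one-sided exact 95% upper limit (61.8% at 24 event-free), so that any later 29-day benchmark can be compared directly.
4. Compare with the standard schedule only if a first-29-day rate of about 62% or more for that schedule is cited. If a source shows that 62% is already such a rate, cite it; the rule then needs no further change.

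The cost is a wording amendment, one extra reported limit and a narrower headline claim. No patients or data are added, and power against the 62% null stays at 91.8%. Moving the null instead would be expensive: at 54%, 47 patients would need 28 event-free, with power of 58.6% at a 40% rate, and 90% power would need 112 patients. The documents give no 29-day rate on which to base such a change.

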15.3 Data Analysis Plan

Patient characteristics and adverse events profiles will be summarized by descriptive statistics. AE rate, ORR, CBR will each be estimated accompanied with 95% confidence interval (CI). PFS will be analyzed by Kaplan-Meier method and 1-year PFS rate will be estimated with 95% CI. All analyses will be conducted among all patients, as well as by subgroups of interest (e.g., line of therapy).

TK1 serum marker will be correlated with absolute neutrophil count along measured time points and tumor response by Pearson or Spearman correlation coefficient as appropriate.

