3.0 PATIENT SELECTION

3.1 Inclusion Criteria

1. Histologically confirmed metastatic ER+ and/or PR+ and HER2- breast cancer who are candidates for palbociclib in combination with either letrozole or fulvestrant per treating physician.
2. Presence of measurable or non-measurable disease by RECIST 1.1 criteria.
3. One prior systemic therapy in the metastatic setting is allowed, but patients who have not had any prior systemic therapies in the metastatic setting are also eligible.
 - Note: patients who were started on endocrine therapy monotherapy as their 1st line or 2nd line systemic therapy in the metastatic setting for no more than 28 days and without clinical progression prior to the initiation of the study drug therapy are allowed to enroll on the study as their 1st line or 2nd line therapy, respectively.
4. At least 18 years of age.
5. ECOG performance status ≤ 2 (see Appendix A)

6. Normal bone marrow and organ function as defined below:
 - a. Absolute neutrophil count $\geq 1,500/\text{mcl}$
 - b. Platelets $\geq 100,000/\text{mcl}$
 - c. Total bilirubin $\leq \text{IULN}$ or total bilirubin $\leq 3.0 \times \text{IULN}$ with direct bilirubin within normal range in patients with documented Gilbert's syndrome
 - d. AST(SGOT)/ALT(SGPT) $\leq 1.5 \times \text{IULN}$ (up to $5 \times \text{IULN}$ in patients with liver disease)
 - e. Creatinine $\leq \text{IULN}$ OR creatinine clearance $\geq 60 \text{ mL/min/1.73 m}^2$ for patients with serum creatinine levels above institutional normal (IULN) (calculated by Creatinine Clearance Estimate by Cockcroft-Gault Equation)
7. Pre- or post-menopausal women are allowed. If pre- or peri-menopausal, concurrent ovarian suppression for pre- or peri-menopausal women is required.
8. Women of childbearing potential must agree to use adequate contraception (hormonal or barrier method of birth control, abstinence) prior to study entry and for the duration of study participation. Should a woman become pregnant or suspect she is pregnant while participating in this study, she must inform her treating physician immediately.
9. Able to swallow and retain oral medication.
10. Washout of at least 3 weeks from prior chemotherapy or targeted therapy that induces myelosuppression and recovery of treatment related adverse events to grade 1 or less, with the exception of alopecia, is required prior to the start of palbociclib.

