5.2 Evaluability

All patients who receive any study treatment are evaluable for toxicity. Patients are evaluated from first receiving study treatment until a 30-day follow up after the conclusion of treatment or death.

All patients are evaluable for disease response unless they discontinue treatment due to treatment related adverse events(s) prior to completion of a first disease assessment.

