Target lesions: All measurable lesions up to a maximum of 2 lesions per organ and 5 lesions in total, representative of all involved organs, should be identified as target lesions and recorded and measured at baseline. Target lesions should be selected on the basis of their size (lesions with the longest diameter), be representative of all involved organs, but in addition should be those that lend themselves to reproducible repeated measurements. It may be the case that, on occasion, the largest lesion does not lend itself to reproducible measurement in which circumstance the next largest lesion which can be measured reproducibly should be selected. A sum of the diameters (longest for non-nodal lesions, short axis for nodal lesions) for all target lesions will be calculated and reported as the baseline sum diameters. If lymph nodes are to be included in the sum, then only the short axis is added into the sum. The baseline sum diameters will be used as reference to further characterize any objective tumor regression in the measurable dimension of the disease.

Non-target lesions: All other lesions (or sites of disease) including any measurable lesions over and above the 5 target lesions should be identified as non-target lesions and should also be recorded at baseline. Measurements of these lesions are not required, but the presence, absence, or in rare cases unequivocal progression of each should be noted throughout follow-up.

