12.4 Response Criteria

12.4.1 Evaluation of Target Lesions

Complete Response (CR): Disappearance of all target lesions. Any pathological lymph nodes (whether target or non-target) must have reduction in short axis to <10 mm.

Partial Response (PR): At least a 30% decrease in the sum of the diameters of target lesions, taking as reference the baseline sum diameters.

Progressive Disease (PD): At least a 20% increase in the sum of the diameters of target lesions, taking as reference the smallest sum on study (this includes the baseline sum if that is the smallest on study). In addition to the relative increase of 20%, the sum must also demonstrate an absolute increase of at least 5 mm. (Note: the appearance of one or more new lesions is also considered progressions).

Stable Disease (SD): Neither sufficient shrinkage to qualify for PR nor sufficient increase to qualify for PD, taking as reference the smallest sum diameters while on study.

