12.4.2 Evaluation of Non-Target Lesions

Complete Response (CR): Disappearance of all non-target lesions and normalization of tumor marker level. All lymph nodes must be non-pathological in size (<10 mm short axis).

Note: If tumor markers are initially above the upper normal limit, they must normalize for a patient to be considered in complete clinical response.

Non-CR/Non-PD: Persistence of one or more non-target lesion(s) and/or maintenance of tumor marker level above the normal limits.

Progressive Disease (PD): Appearance of one or more new lesions and/or unequivocal progression of existing non-target lesions. Unequivocal progression should not normally trump target lesion status. It must be representative of overall disease status change, not a single lesion increase.

Although a clear progression of “non-target” lesions only is exceptional, the opinion of the treating physician should prevail in such circumstances, and the progression status should be confirmed at a later time by the review panel (or Principal Investigator).

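### The overall response rate is estimated in all patients, although patients with only non-measurable disease can count as responders by CR but never by PR

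*Combined protocol and SAP*

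**What the plan says.** - **Endpoint.** Section 2.2, item 5: "To determine the overall response rate (CR+PR) in patients with hormone receptor positive breast cancer".
- **Estimation.** Section 15.3: "AE rate, ORR, CBR will each be estimated accompanied with 95% confidence interval (CI"). No test and no reference rate is attached to ORR.
- **Population.** Section 15.3: "All analyses will be conducted among all patients, as well as by subgroups of interest (e.g., line of therapy"). Line of therapy is the only subgroup named.
- **Eligibility.** Section 3.1, item 2: "Presence of measurable or non-measurable disease by RECIST 1.1 criteria". The non-measurable share is not capped.
- **Partial response.** Section 12.4.1: "At least a 30% decrease in the sum of the diameters of target lesions, taking as reference the baseline sum diameters". Section 12.2 draws target lesions only from measurable ones: "All measurable lesions up to a maximum of 2 lesions per organ and 5 lesions in total". It classes bone lesions and effusions, among others, as non-measurable.
- **Non-measurable disease.** The second table in 12.4.3 allows CR, non-CR/non-PD, not evaluated and PD. It has no PR row.
- **Evaluability.** Section 5.2: "All patients are evaluable for disease response unless they discontinue treatment due to treatment related adverse events(s") before a first disease assessment is complete. Measurability is not mentioned.

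**The concern.** A patient with no measurable lesion enters the ORR denominator but can reach the numerator only if all disease disappears. A patient with measurable disease can also get there with a 30% shrinkage. Pooling the two groups gives a rate that moves with the mix of patients enrolled, even when drug activity in measurable disease is constant.

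This matters for two reasons. The trial has no control arm, so ORR has no internal comparator with the same mix. And 15.3 plans the analyses by line of therapy: if first- and second-line patients differ in how often their disease is non-measurable, their ORRs will differ for that reason alone. If the denominator is left open until the data are seen, the choice can also follow the result.

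The point concerns ORR only.

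**Working it through.** **1. The plan's own figures.** The documents state no expected ORR, no ORR precision and no non-measurable share, so there is no ORR figure to reproduce. The all-patient denominator is N=47 from 15.2. With 24 or more of 47 patients free of the event as the success rule, the exact binomial tail is 0.0466 at a rate of 0.38 and 0.9181 at 0.60. These match the stated alpha of 4.7% and power of 91.8%. Nothing below changes them.

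**2. Formula.** Let f be the non-measurable share, R the ORR in measurable disease and C the CR rate in non-measurable disease. Then

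all-patient ORR = (1 − f) × R + f × C.

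f, R and C are all assumptions.

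**3. Results with C = 0.**

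| f | R = 45% | R = 40% |
|---|---|---|
| 10% | 0.9 × 45 = 40.5% | 36% |
| 20% | 0.8 × 45 = 36% | 32% |
| 30% | 0.7 × 45 = 31.5% | 28% |
| 40% | 0.6 × 45 = 27% | 24% |

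At f = 30%, the all-patient ORR is 21% if R = 30% and 35% if R = 50%.

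**4. Does the CR route close the gap?** Take C = 5%, f = 30% and R = 40%: 0.7 × 40 + 0.3 × 5 = 29.5%, against 28% with C = 0. The gap to 40% remains.

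**5. One data set, two denominators.** With f = 30%, about 33 of 47 patients are measurable (47 × 0.7 = 32.9). Suppose 13 of them respond and no non-measurable patient does.
- All patients: 13/47 = 27.7%, Clopper-Pearson 95% CI 15.6–42.6%.
- Measurable disease: 13/33 = 39.4%, Clopper-Pearson 95% CI 22.9–57.9%.

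**6. Line-of-therapy subgroups.** With R = 45% in both lines and C = 0, f = 20% in one line and 40% in the other gives 36% and 27%. That is a 9-point difference with no difference in activity.

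**7. Precision after the change.** The normal-approximation half-width is 1.96 × √(p(1 − p)/n).
- All patients, 35 of 47 measurable, R = 45%: p = 0.45 × 35/47 = 33.5%; half-width 13.5 points.
- Measurable only, n = 35, p = 45%: 16.5 points.
- Measurable only, n = 28 (f = 40%), p = 45%: 18.4 points.
- First line: 15.2 expects about 14 patients; at f = 30% about 10 remain (14 × 0.7 = 9.8), giving about 31 points.

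**The case against.** The strongest reply is that the plan's quantity is legitimate. Section 2.2 defines ORR in the treated population and 15.3 estimates it there, so the all-patient proportion is unbiased for what the plan says it estimates. A measurable-disease denominator is a different estimand, not the correction of an error. The plan gives no ORR benchmark (15.2 benchmarks only neutropenia and clinical benefit), so any mismatch with outside rates arises in a comparison that the plan does not make. The subgroup list in 15.3 is open-ended, so a measurable-disease ORR could be reported under the present text.

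Most of this stands. A reader might call the all-patient ORR biased; for the stated estimand it is not. What remains is interpretability: the figure mixes two groups with different routes to response, the mix is unknown, and permission to run a subgroup is not prespecification.

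A reader might also infer that CR is effectively closed to non-measurable patients. Section 12.4.2 requires "Disappearance of all non-target lesions and normalization of tumor marker level", and the study calendar in Section 10.0 schedules no marker. The documents do not support that inference. The note in 12.4.2, and the tumor-marker paragraph in 12.3, require normalization only when markers are raised at the start. The condition also applies to measurable patients with non-target lesions. CR stays possible, and the point does not need the marker argument.

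**Conclusion.** The point holds as one of interpretation and prespecification. Following 15.3 as written gives an ORR diluted by the non-measurable share. With 45% ORR assumed in measurable disease and no CR elsewhere, the reported rate would lie between 40.5% and 27% for assumed shares of 10% to 40%. At a 30% share it would be 31.5%, or 28% if the measurable-disease ORR is 40%. These are illustrations, because neither input is in the documents.

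It would go too far to say that the all-patient ORR reflects case mix instead of drug activity. It still rises and falls with activity in measurable disease, and CR counts in everyone. ORR is secondary, descriptive and carries no decision rule, so the primary neutropenia test, its cut-off and N=47 are untouched.

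**What to change.** In 15.3, state that ORR is reported with an exact 95% CI in patients with measurable disease at baseline, that the all-patient ORR is supportive, and that the non-measurable share is tabulated overall and by line of therapy.

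Align 5.2 with this. At present 5.2 removes some early discontinuations from the response-evaluable group, 15.3 refers to all patients, and neither mentions measurability. One response denominator should be named in both places.

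No extra data, visits or patients are needed: Section 11.0 already schedules a baseline tumor measurement form. The cost is precision. At an assumed 45% ORR, the half-width is about 16.5 points with 35 measurable patients and 18.4 with 28, against about 13.5 for the all-patient figure when 35 of 47 are measurable. In the first-line subgroup, about 14 patients before any restriction, the interval will be much wider and the estimate should be labelled descriptive.
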